8 SAFETY

Safety will be evaluated based on data collected for AEs, clinical laboratory data, vital signs, electrocardiogram (ECG) data, and physical examinations.

All safety analysis reporting will be based on the Safety Population. No formal statistical testing will be conducted for the safety analyses. Descriptive statistics will be used to evaluate safety data in this study. Summaries will present data by treatment group and overall. Listings will list safety data by treatment group and subject.

8.1 Adverse Events

An AE is any symptom, sign, illness, or experience that develops or worsens in intensity during the course of the study. Any newly developed illnesses or injuries should be regarded as adverse events. AEs will be assessed for severity, relationship to study drug, and seriousness. Further details about AE determination and categorization can be found in the study protocol.

Serious adverse events (SAEs) will be recorded starting at Visit 1 after signing informed consent. AEs will be recorded from the time of first IP administration through end of study. A TEAE is defined as any AE occurring on or after start of IP. All summaries of AEs will be based on TEAEs. All AEs recorded on the eCRF, whether treatment-emergent or not, will be presented in a data listing. Non-TEAEs will be flagged in the listings.

All AE data will be reported for two time periods: prior to Visit 3 dosing, and during or after Visit 3 dosing. This is due to the fact that all subjects receive [REDACTED] at Visit 2 and then receive randomized treatment [REDACTED] at Visit 3. AEs will be assigned to a time period based on AE start date. An AE that starts on the day of Visit 3 dosing will be assigned as “during or after Visit 3 dosing”. From Screening until IP administration at Visit 2, any clinically significant abnormality should be recorded as a preexisting condition in the medical history, not as an AE.

All AE terms will be coded by using MedDRA, version 24.0 – Mar 2021.

Missing and partially missing start and/or end dates will be imputed for the purpose of determining treatment-emergent flags and AE categorization, according to Section 5.7.

The incidence of TEAEs will be summarized by maximum severity and strongest relationship to IP. When calculating the incidence of TEAEs, each TEAE will be counted only once for a given subject within a MedDRA category (i.e., overall, SOC, or PT). When TEAEs are summarized within levels of another TEAE assessment (i.e., severity or relationship), TEAEs will be counted once per subject at the worst level of the assessment (i.e., greatest severity or relationship to IP). Any missing severity assessments will be assumed to be severe and missing relationship assessments will be assumed to be related.

An overview summary table of TEAEs will be produced, including counts and percentages of subjects with any incidences of: TEAEs, TEAEs by maximum severity, TEAEs by relationship to IP, TEAEs leading to study discontinuation, TEAEs leading to death, TEAEs related to IP leading

to death, serious TEAEs and serious TEAEs by maximum relationship to IP, serious TEAEs leading to study discontinuation and serious TEAEs leading to death.

In addition to the overview of TEAEs, the following summaries of TEAEs will be produced:

- TEAEs by System Organ Class and Preferred Term
- TEAEs by System Organ Class, Preferred Term and Maximum Severity
- TEAEs by System Organ Class, Preferred Term and Relationship to IP
- Severe TEAEs by System Organ Class and Preferred Term
- Serious TEAEs by System Organ Class and Preferred Term
- Serious TEAEs Related to IP by System Organ Class and Preferred Term
- TEAEs Leading to Study Discontinuation by System Organ Class and Preferred Term

Listings for SAEs, AEs leading to death, and AEs leading to study discontinuation will be produced as tables. Finally, all AE data will be presented in a by-subject data listing.

8.2 Clinical Laboratory Evaluations

Hematology, clinical chemistry, urinalysis, and thyroid laboratory tests, along with urine drug screen and pregnancy tests, will be collected at various time points in the study. Hematology, clinical chemistry, urinalysis, and thyroid parameters are scheduled to be collected during screening and at Visit 4. Urine pregnancy and urine drug screen are scheduled to be collected at every visit. Refer to the Schedule of Time and Events in Appendix 1.

Hematology, clinical chemistry, urinalysis, and thyroid parameters will be reported based on the International System of Units (SI). The list of parameters to be collected can be found in the study protocol section 5.4.

Observed values and changes from baseline for laboratory evaluations will be summarized at each visit by treatment group and overall. Laboratory data will also be summarized in shift from baseline tables to display the number and percentage of subjects with clinical laboratory values categorized as low (below the lower limit of normal [LLN]), normal, or high (above the upper limit of normal [ULN]), at each post baseline visit by Visit 3 treatment group.

All laboratory parameters will be presented in a by-subject data listing and values that are outside normal ranges will be flagged. Per the data transfer agreement with ACM, abnormality flags in the data will be as follows: LP=Low Panic, LN=Low Normal, N=Normal, HN=High Normal, HP=High Panic, AB=Abnormal, SC=See Comment. Per ICH E3, an abnormal lab listing will be provided, showing all values for a given lab parameter for a given subject for which at least one abnormal value occurred.

Urine drug screen and pregnancy tests will not be summarized in tables, however their data will be included in a by-subject data listing.

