5.2.2 Visit 2 (Baseline)

For subjects continuing to meet all eligibility criteria, the following Visit 2 assessments will be completed:

- Measure vital signs after the subject has rested for 5 minutes: seated systolic and diastolic blood pressure, heart rate, respiratory rate, and body temperature.
- Obtain urine sample for Urine Drug Screen: Instant Exam to be performed on site, with results thoroughly documented in the source; urine sample to be sent to central laboratory for confirmation if on-site UDS is positive [REDACTED]
[REDACTED].

- For females of child-bearing potential, obtain urine sample and complete on-site urine pregnancy test.
- Record concomitant medication use including the completion of any washout.
- Review all inclusion and exclusion criteria.

For subjects meeting all study inclusion criteria and no study exclusion criteria, the following Visit 2 procedures will be performed:

[figure not shown]
- Introduce the self-rated anxiety scale, the Subjective Units of Distress Scale (SUDS), to the subject and review the descriptions of the various SUDS scores (Appendix A).
- [REDACTED]
- Dispense and instruct subject to self-administer IP [REDACTED]
[REDACTED]
- The subject will be returned to a waiting area after IP dosing.
- [REDACTED] the subject will be informed that they must give a 5-minute speech to a live audience of [REDACTED]
[REDACTED]
- [REDACTED]
[REDACTED]
[REDACTED]
- The subject will be given 3 minutes to organize their thoughts on their upcoming speech.
- The subject will be escorted into a room to give a 5-minute speech in front of three neutral observers after the last SUDS anticipatory anxiety score is collected
[REDACTED]
[REDACTED]
[REDACTED]
[REDACTED]

- [REDACTED]

[REDACTED], the subject will be given information on attending the next visit (Visit 3), else the subject will complete the remaining assessments for Visit 2, will not be randomized, and will be discharged from the study [REDACTED]

- If the subject cannot complete the speech due to anxiety levels, the SUDS level will be requested from them before they leave the room and all remaining time points will be marked as not done.
- Record any AEs reported.
- [REDACTED]

For the subject attending the next visit (Visit 3), it will be scheduled 1 week (\pm 2 days) after the date of Visit 2.

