5.2.3 Visit 3 (Treatment)

At Visit 3, subjects should return to the study site and the following assessments will be completed:

- Measure vital signs after the subject has rested for 5 minutes: seated systolic and diastolic blood pressure, heart rate, respiratory rate, and body temperature.
- Urine Drug Screen (Instant Exam, to be performed on site, with results documented in the source).
- Record Concomitant Medication use.
- Review and record AEs.
- Randomize the subject.
- [REDACTED] follow the instructions for the Visit 3 public speaking challenge (as described in Section 5.2.2 and Figure 5-1) with the same trained observer as in Visit 2.

After the completion of the Visit 3 public speaking challenge:

- [REDACTED]
- Complete the CGI-I (by the trained observer of the public speaking challenge).
- Review and record AEs.
- Administer C-SSRS (Since Last Visit) [REDACTED]

The Follow-Up visit (Visit 4) will be scheduled for 1 week ± 2 days after the date of Visit 3.

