8.2.4.2 Safety Procedures

Safety in this Study will be determined from evaluation of AEs, clinical laboratory assessments, vital signs assessments, changes in suicidality (C-SSRS) and level of depression (HAM-D), physical examinations including examination of the nasal passages, and ECGs. Specific visits for obtaining clinical laboratory assessment samples are listed in the Schedule of Time and Events ([Table 5-1](#)). The schedule of clinical laboratory tests is listed in Section [5.4](#).

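### SAP 8.2 schedules a urine pregnancy test at every visit, but the protocol's Visit 3 list shows none before randomization at the only PH94B dosing visit

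*SAP*

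**What the plan says.** SAP 8.2 (Clinical Laboratory Evaluations) gives one schedule for two urine tests: "Urine pregnancy and urine drug screen are scheduled to be collected at every visit". It then points to the schedule table, "Refer to the Schedule of Time and Events in Appendix 1", and says how the results are reported: "Urine drug screen and pregnancy tests will not be summarized in tables, however their data will be included in a by-subject data listing".

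The protocol sets out procedures visit by visit. Sections 5.2.1 (Visit 1), 5.2.2 (Visit 2) and 5.2.4 (Visit 4) each carry an explicit line for the pregnancy test. At Visit 2 it reads "For females of child-bearing potential, obtain urine sample and complete on-site urine pregnancy test". Section 5.2.3 (Visit 3) has no such line. Its only urine test before randomization is "Urine Drug Screen (Instant Exam, to be performed on site, with results documented in the source".

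Other provisions on the point:

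- Inclusion criterion 6 requires negative urine tests at Visits 1 and 2.
- Exclusion criterion 11 bars women with a positive test before investigational product (IP) is given, and names no visit.
- Protocol 5.4 lists the on-site pregnancy test without naming visits.
- Protocol 8.2.4.2 leaves sampling visits to the schedule: "Specific visits for obtaining clinical laboratory assessment samples are listed in the Schedule of Time and Events".
- SAP section 2 gives the Visit 2 treatment as placebo, and SAP 5.2 says PH94B is first given at Visit 3.

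**The concern.** Sites carry out visits from the visit lists, and here the list and the SAP differ at the visit where it matters most. As written, the lists put a pregnancy test before the placebo dose and another a week after the randomized dose, but none on the day PH94B is given. A site following 5.2.3 alone would randomize a woman of child-bearing potential on the strength of a test about a week old.

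The protocol treats reproductive exposure as something to manage. It requires contraception and negative tests before dosing, has women stop breastfeeding from Visit 2 to Visit 4, and requires any pregnancy with possible fetal exposure to be reported (6.5.3). A same-day test would lower the chance of dosing a pregnancy that has become detectable since Visit 2. It would not date conception and would not change when a report under 6.5.3 is due.

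There is a smaller reporting consequence. If sites follow 5.2.3, the by-subject listing in SAP 8.2 will have no Visit 3 pregnancy results, although the SAP says they are collected.

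**Working it through.** No sample size, power or alpha figure is involved. The check compares the texts and does one piece of date arithmetic.

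**Step 1. Urine tests by visit.**

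| Visit | Protocol section | Drug screen listed | Pregnancy test listed |
|---|---|---|---|
| 1 | 5.2.1 | yes | yes |
| 2 | 5.2.2 | yes | yes |
| 3 | 5.2.3 | yes | no |
| 4 | 5.2.4 | yes | yes |
| Total | | 4 of 4 | 3 of 4 |

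The SAP sentence implies 4 of 4 for both. It matches the visit lists for the drug screen and not for the pregnancy test.

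**Step 2. Could redaction explain the gap?** The first five bullets of 5.2.3 are all legible: vital signs, drug screen, concomitant medication, adverse events, and "Randomize the subject". Redaction starts only after that, so it does not hide a test before randomization. The cross-reference to 5.2.2 that follows concerns how the speaking challenge is run, not the Visit 2 eligibility checks.

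**Step 3. Does another provision order a Visit 3 test?** Inclusion 6 names Visits 1 and 2 only. Exclusion 11 says what a positive result means but schedules no test. Section 5.4 names the test but no visit. Visit 2 includes a review of the entry criteria; the legible Visit 3 bullets do not.

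**Step 4. Age of the last listed test at PH94B dosing.** Protocol 5.2.2 gives the timing: "For the subject attending the next visit (Visit 3), it will be scheduled 1 week", with a window of 2 days either way. So 7 − 2 = 5 days and 7 + 2 = 9 days. On the visible lists the last test before PH94B is 5 to 9 days old.

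**Step 5. What the analysis loses.** Pregnancy results go to a listing and not to tables. They do not enter the ANCOVA on the Subjective Units of Distress Scale (SUDS), the comparison of response proportions on the Clinical Global Impression Scale of Improvement (CGI-I), or the adverse event tables. Efficacy, power and type I error are unaffected.

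I give no expected number of pregnancies. The documents state neither the share of women of child-bearing potential nor a pregnancy rate on contraception, and a figure built on guesses for both would say nothing beyond 'small'.

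**The case against.** The strongest objection is that the deciding page is not in hand. SAP 8.2 and protocol 8.2.4.2 both defer to the Schedule of Time and Events, which is missing from the text available for review. The SAP sentence is itself evidence that the schedule marks Visit 3. If it does, the plan already contains the test, and the defect is one omitted bullet. This stands, and it limits the point. It does not remove it: if Table 5-1 marks Visit 3, then 5.2.3 disagrees with it and a site working from the list could miss the test; if it does not, the SAP sentence is wrong.

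Second, redaction is ruled out only up to randomization. Between randomization and dosing there is redacted text in 5.2.3, a redacted bullet just before dispensing in 5.2.2, and a figure that is not shown. A pregnancy test there is unlikely, but the 5 to 9 day figure rests on the visible lists.

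Third, there is other protection. Contraception and two negative tests are required. Exclusion 11 can be read as covering the Visit 3 dose, because protocol 4.2.2 has IP given before each challenge, and SAP 5.5 ties Visit 3 randomization to eligibility. A positive result found at Visit 3 could therefore be acted on. None of this orders the test.

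Fourth, nothing in the documents shows that testing at Visits 1, 2 and 4 is inadequate for a single 3.2 µg intranasal dose, and a Visit 3 test would most likely find nothing. That is fair. The case for the test is that the sponsor's own SAP says it is scheduled, and that it costs very little.

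**Conclusion.** The conflict is real and narrow. SAP 8.2 says every visit; the protocol's visit lists give the pregnancy test at 3 of 4 visits, and the gap falls before randomization at the only PH94B dosing visit. On those lists the last test is 5 to 9 days old and was done before placebo. This assumes that the redacted text after randomization and the unseen schedule add no test.

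A reader might infer that the trial plans to give PH94B without a same-day pregnancy test, or that it exposes participants to a material pregnancy risk. The documents support neither. The schedule may include the test. The absolute risk is very small given contraception, two negative tests and one microgram-level intranasal dose; protocol 1.3 adds that PH94B could not be quantified in blood in a Phase 1 trial, although the dose there is redacted. No efficacy result or tabulated safety result changes. This is a cheap safety improvement, not a flaw in the trial's inference.

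**What to change.** First check Table 5-1 and SAP Appendix 1. Then add one bullet to protocol 5.2.3, ahead of the randomization step, along these lines: *Women of child-bearing potential: on-site urine pregnancy test; if positive, do not randomize or dose.* Mark Visit 3 in the schedule if it is not marked already. SAP 8.2 then stands as written.

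The position matters. The ITT population is everyone randomized (protocol 8.2.1.1), so a positive test found after randomization would leave a randomized, undosed subject with no Visit 3 SUDS, whose primary endpoint would need imputing under SAP 5.6.

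The cost is one dipstick per woman of child-bearing potential, on urine already collected that day for the drug screen. The new bullet also needs a protocol amendment with sponsor and IRB approval, which the investigator agreement at the front of the protocol requires; it can be bundled with the next amendment. SAP 7.1.2.1 already names individual subjects, so enrollment had begun and the change would help only those not yet at Visit 3.

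If the sponsor decides against testing at Visit 3, SAP 8.2 should say that the pregnancy test is done at Visits 1, 2 and 4. That corrects the record but adds no protection.

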8.3 Vital Signs and Physical Examinations

Vital signs will be collected at all visits. Physical examinations will be performed at Visit 1 and Visit 4. Refer to the Schedule of Time and Events in Appendix 1.

Vital signs collected at all visits will include temperature, heart rate, respiratory rate, systolic blood pressure, and diastolic blood pressure. Height and weight will be collected at Visit 1 and will be summarized and listed with Demographics and Baseline Characteristics data. For other vital signs parameters, observed values and changes from baseline (as applicable) will be summarized for each visit. Vital signs data will also be presented in a by-subject data listing.

Significant findings from physical examinations will be recorded with medical history or adverse events. Physical examination data will be listed.

8.4 Electrocardiograms (ECGs)

Electrocardiogram (ECG) data is scheduled to be collected at Visit 1 and Visit 4.

Collected ECG parameters include ventricular rate, RR interval, PR interval, QRS interval, QT interval, QTc interval, and an assessment for whether the ECG results were normal, abnormal not clinically significant, or abnormal clinically significant. The QT interval corrected using the Fredericia formula (QTcF) will be calculated as $QTcF = QT/RR^{1/3}$, where QT is measured in msec and RR is measured in sec. (Note that RR is collected in msec and will need to be converted to sec.) Observed values and changes from baseline for quantitative ECG parameters will be summarized at each visit. Qualitative results will also be summarized.

All ECG data will be presented in a by-subject data listing.

8.5 Columbia Suicidality Severity Rating Scale (C-SSRS)

C-SSRS data is scheduled to be collected at the end of every visit. The C-SSRS questionnaire given at Visit 1 will ask subjects to report on ideation and behavior over the past six months. The C-SSRS questionnaire given at other visits will ask subjects to report on ideation and behavior since the last visit.

The C-SSRS will be scored in the following way:

- *suicidal ideation indicator*: if the response to any one of the five suicidal ideation questions below is “Yes”, then set the suicidal ideation indicator equal to 1. Otherwise set the suicidal ideation indicator equal to 0.
 - Wish to be Dead
 - Non-specific Active Suicidal Thoughts
 - Active Suicidal Ideation with Any Methods (Not Plan) without Intent to Act
 - Active Suicidal Ideation with Some Intent to Act, without Specific Plan

- Active Suicidal Ideation with Specific Plan and Intent
- *suicidal behavior indicator*: if the response to any one of the five suicidal behavior questions below is “Yes”, then set the suicidal behavior indicator equal to 1. Otherwise set the suicidal behavior indicator to 0.
 - Preparatory Acts or Behavior
 - Aborted Attempt
 - Interrupted Attempt
 - Actual Attempt (nonfatal)
 - Completed Suicide
- *suicidal ideation or behavior indicator*: if the response to any one of the five suicidal ideation questions or any one of the five suicidal behavior questions above is “Yes”, then set the suicidal ideation or behavior indicator equal to 1. Otherwise set the suicidal ideation or behavior indicator to 0.

The number and percentage of subjects with each of the indicators and individual items above will be summarized by visit and Visit 3 treatment group. Subjects indicating self-injurious behavior without suicidal attempt will also be summarized. C-SSRS data will be provided in a by-subject listing.

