3.3.3 Safety

Safety and tolerability of PH94B will be assessed and summarized through changes from Screening in laboratory values, ECGs, physical examinations, and vital sign assessments following exposure to PH94B, as well as by comparison of AEs, suicidal ideation (C-SSRS), and level of depression (HAM-D) reported during treatment with PH94B and placebo.

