5.2 Reference Dates and Definitions

The reference dates for this study are as follows:

- Informed consent date is defined as the eCRF-provided date on which a subject signed the informed consent form.
- Randomization date is defined as the date on which the subject is randomized to study treatment.
- Treatment start date is defined as the date of first dose of IP including dosing of [REDACTED] at Visit 2.

- Treatment end date is defined as the date of last dose of IP.
- The calculation of age will use the informed consent date as its reference date.
- Safety Population data, such as AEs and laboratory assessments, will use the treatment start date as a reference date. In this study, because first dose of PH94B will not occur until Visit 3, AEs will be reported for both prior to Visit 3 IP administration and post.
- Study day will be based on treatment start date as a reference date.

Variable	Definition
Baseline Value	Baseline may refer to the last non-missing value [REDACTED]
Post-Baseline Value	Defined as values collected after IP administration.
Change from Baseline	Defined as: Post-Baseline Value – Baseline Value
Percent Change from Baseline	Defined as: (Value at Post-baseline Visit – Value at Baseline)/Value at Baseline x 100. Note: To compute percent change from baseline, the baseline value cannot be equal to zero.
Temperature (in °C)	= (temperature (in °F) - 32) * 5/9
Height (in cm)	= height (in inches) * 2.54
Weight (in kg)	= weight (in lbs) * 0.4536

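### Does showing the Visit 3 C-SSRS by Visit 3 treatment group, with no new-or-worse measure at Visit 4, misstate suicidality on PH94B?

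*SAP*

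**What the plan says.** SAP 8.5 fixes the timing: "C-SSRS data is scheduled to be collected at the end of every visit". It gives two recall windows. For screening, "The C-SSRS questionnaire given at Visit 1 will ask subjects to report on ideation and behavior over the past six months". After that, "The C-SSRS questionnaire given at other visits will ask subjects to report on ideation and behavior since the last visit". It defines three yes/no indicators (ideation, behavior, either) and states that these and the "individual items above will be summarized by visit and Visit 3 treatment group". A by-subject listing is also planned.

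Protocol 5.2.3 lists the since-last-visit form among the steps after the Visit 3 speech. Protocol 5.2.2 places Visit 3 one week, plus or minus 2 days, after Visit 2; 5.2.3 places Visit 4 at the same interval after Visit 3.

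For adverse events the SAP separates the periods before and after Visit 3 dosing. SAP 5.2 gives the reason, "because first dose of PH94B will not occur until Visit 3", and SAP 8.1 gives the rule: "AEs will be assigned to a time period based on AE start date". Section 8.5 has no counterpart. On purpose, Protocol 2.4 and 8.2.4.2 name changes in suicidality, and Protocol 3.3.3 calls for a comparison of "suicidal ideation (C-SSRS), and level of depression (HAM-D) reported during treatment with PH94B and placebo". SAP 8 adds: "No formal statistical testing will be conducted for the safety analyses".

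**The concern.** A subject with suicidal ideation in the week before Visit 3 dosing answers yes on the Visit 3 form and is then counted under PH94B or placebo, although no PH94B had been given when the ideation occurred. Positive answers should be rare, so one or two such subjects could be taken for a drug effect or, if they fall in the placebo arm, for reassurance.

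There is a second gap. A count of positives at Visit 4 does not by itself show whether the ideation is new, worse or continuing, yet the protocol speaks of change. The laboratory, vital-sign and ECG sections of the SAP all plan change from baseline; 8.5 does not mention a baseline. Suicidality is part of the safety objective, so attribution matters.

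**Working it through.** The documents give no figure for the pre-dose share, so there is none to reproduce.

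**Inputs**
- W, Visit 2 to Visit 3: 7 ± 2 days, so 120, 168 or 216 h (Protocol 5.2.2).
- t, Visit 3 dose to C-SSRS form: not in the visible text. The visible steps after dosing are 3 min of preparation and a 5 min speech, so at least 8 min. Assumed range 0.5 to 8 h for a same-day visit.
- 104 subjects per arm (protocol synopsis, statistical methods).

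**Share of the Visit 3 window before PH94B** = 1 − t/W

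| W | t = 8 min | 0.5 h | 2 h | 4 h | 8 h |
|---|---|---|---|---|---|
| 5 days | 99.9% | 99.6% | 98.3% | 96.7% | 93.3% |
| 7 days | 99.9% | 99.7% | 98.8% | 97.6% | 95.2% |
| 9 days | 99.9% | 99.8% | 99.1% | 98.1% | 96.3% |

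For example, 1 − 8/120 = 93.3% and 1 − 0.5/216 = 99.8%. Visits are scheduled by date, so the shortest interval could be somewhat under 120 h; at an assumed 112 h with t = 8 h the share is 1 − 8/112 = 92.9%. The description "almost all" in plain words is safe; any narrower figure rests on t.

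**Visit 4 window.** It runs from the end of Visit 3 to Visit 4, 5 to 9 days, and 0% of it is before Visit 3 dosing. It has its own row, by group.

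**Can the pre-dose part bias the Visit 3 row?** Subjects are randomized at Visit 3, after the pre-dose interval has passed. Ideation in that interval cannot depend on the assigned arm, so the pre-dose part adds chance noise and no systematic difference.

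**How many subjects?** The documents give no rate. Assuming 0.2% to 1% positive per week, the expected number per arm over 7 days is 104 × 0.002 = 0.2 to 104 × 0.01 = 1.0. For two independent binomial counts at those rates, the arms differ by 2 or more in 3.1% to 26.9% of trials. With the same rate and a 7-day window the Visit 4 row gives identical figures. They describe any rare event in two arms of 104 and do not measure a harm from the timing of the Visit 3 form.

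**Is a change measure required?** Protocol 2.4 and 8.2.4.2 name change without defining it. Protocol 3.3.3 and SAP section 2 tie change from Screening to laboratory values, vital signs, ECGs and physical examinations, and list the C-SSRS separately with adverse events and HAM-D. By-visit counts by group meet that wording.

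**Would a new-or-worse table be straightforward?** It depends on the reference.
- Visit 3 as reference: ideation that starts after Visit 3 dosing, is reported that day and persists unchanged to Visit 4 would be classed as not new. The table would remove the very case it is meant to find.
- Visit 1 as reference: on the SAP's six months (about 183 days) its recall is 183/9 = 20 to 183/5 = 37 times the Visit 4 window, so the two rows are not comparable.
- Visit 2 avoids the first problem, and the planned listing already allows that comparison for each subject.

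**The case for a change.** The strongest case for a change is consistency. The SAP sees that randomized exposure starts at Visit 3 and splits adverse events there, yet shows the C-SSRS for a mainly pre-dose interval under treatment headings with no note. A listing lets a careful reader rebuild the sequence but is not a summary of change. Rare counts are read by eye, and footnotes plus one descriptive table would use data already collected.

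The facts in this stand: the Visit 3 window is almost wholly pre-dose, and 8.5 has neither a label nor a new-or-worse category. The inference is weaker. Visit 3 treatment group is the general column heading set in SAP 5.1, and the Visit 1 and Visit 2 C-SSRS rows sit under it without anyone reading them as drug effects. Section 8.5 states the recall window and collection time itself, so a reader of the section has what is needed to interpret the row. The adverse-event rule works from a start date, whereas a C-SSRS answer covers an interval and the visible text gives it no onset date, so the rule does not carry over directly. Calling the Visit 3 row purely pre-treatment would also be wrong: that form holds the only immediate post-dose C-SSRS time in a single-dose study.

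**Conclusion.** No change to the plan is needed. Followed as written, SAP 8.5 gives correct descriptive counts: separate rows by visit, a Visit 4 row wholly after Visit 3 dosing, grouping by treatment received (SAP 4.3), no hypothesis test and a listing that resolves each rare case. A note of each row's recall window is something an analyst can put under the table without amending the SAP; it would correct no wrong rule or result. Efficacy is not touched.

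The size is a possible misreading of a few responses. The pre-dose share of about 93% or more assumes that the form is completed within 8 h of the Visit 3 dose. The 0.2 to 1.0 positives per arm assumes a weekly rate of 0.2% to 1%, which has no source in the documents; the entry exclusions for suicide risk may make it lower. The SAP 5.2 baseline definition and the protocol text after the Visit 3 C-SSRS instruction are partly blacked out, so a relevant baseline or timing rule may exist that cannot be seen. The conclusion does not depend on there being one.
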